6.3.2. Analysis Methods

Descriptive statistics (mean, standard deviation, median and range) will be provided for the vital signs at each scheduled visit. Changes from baseline will be summarized by treatment group. Incidence of vital signs tests that meet criteria for abnormality will be tabulated for each treatment group.

A cross-tabulation of the worst grade/abnormality versus baseline will be presented for the combination of analysis treatment- and follow-up phase and for analysis treatment phase only. This table will also show the number (n) and percentage (%) of subjects per worst grade/abnormality, the number (n) and percentage (%) of subjects per emergent worst grade/abnormality. For Respiratory rate, heart rate and body temperature, the maximum value will be considered as the worst grade/value while for oxygen saturation, the lowest value will be considered the worst one. In determining the maximum body temperature, all temperature assessments will be considered regardless of whether obtained during on-site visit or measured by caregiver and reported in handheld device.

Mean \pm SE graphs over time for the actual values and changes from baseline will be generated and presented by treatment group and by age group as assigned at Screening.

A listing of abnormal individual subject vital signs values from scheduled and unscheduled timepoints will be provided. This listing will include all other timepoints for the corresponding subject/parameter.

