6.3. Vital Signs and Physical Examination Findings

6.3.1. Definitions

Systolic (SBP) and diastolic blood pressure (DBP), HR, RR, oxygen saturation and body temperature will be investigated. A directed physical examination (DPE) will be performed at several timepoints throughout the study, which includes respiratory system, nose, ear, throat, facial, and neck lymph nodes, and skin examination. Note that heart rate, respiratory rate, oxygen saturation (SpO_2) and body temperature are also analyzed as part of efficacy endpoints.

Definitions Grades/Abnormalities

Two sets of abnormality codes for SBP, DBP, HR, RR and oxygen saturation will be defined, as indicated in [Table 25](#) and [Table 26](#). Vital signs abnormalities will be identified based on subject's age at the time of the assessment and as follows:

- Worst grades/abnormalities are determined over the whole observational period and for each analysis phase separately, including post-baseline scheduled and unscheduled measurements of that analysis phase.
- The abnormalities 'abnormally low' and 'abnormally high /grades are considered equally important, i.e. if a subject has as well an abnormally low as an abnormally

high or graded value post-baseline, both abnormalities are shown in the tables. This means that the sum of the percentages can be more than 100%.

Table 25: Normal Ranges – Below/Normal (including extremes)/Above

Parameter (unit)	Age class				
	0 – 3 months	3 – 6 months	6 – 12 months	1 – 2 years	2- <3 years
Diastolic BP (mmHg)	45 - 55	50 - 65	55 - 65	55 - 70	45 - 60
Systolic BP (mmHg)	65 -85	70 - 80	80 - 100	90 - 105	85 - 100
Heart rate HR (bpm)	100 - 150	90 - 120	80 - 120	70 - 110	95 - 125
Respiratory rate	35 - 55	30 - 45	25 - 40	20 - 30	22 - 30
Oxygen saturation	≥96	≥96	≥96	≥96	≥96
SpO ₂ (%)					

Table 26: Relevant Abnormalities – Abnormally Low/Normal/Abnormally High

Parameter (unit)		Age class			
		0 – 3 months	3 – 12 months	1 – 2 years	2- <3 years
Diastolic BP (mmHg)	abnormally low	<35	<40	<40	<40
	abnormally high	>65	>85	>90	>70
Systolic BP (mmHg)	abnormally low	<60	<60	<75	<80
	abnormally high	>110	>110	>120	>110
Heart rate HR (bpm)	abnormally low	<80	<70	<60	<90
	abnormally high	>180	>150	>140	>130
Respiratory rate	abnormally low	<25	<20	<18	<20
	abnormally high	>70	>60	>50	>35
Oxygen saturation	abnormally low	<92	<92	<92	<92
SpO ₂ (%)					

Abnormality codes for body temperature are defined, as indicated in [Table 27](#).

Table 27: Abnormalities for Body Temperature

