Abnormality Code	Temperature (°C)				
	Tympanic	Forehead	Oral	Rectal	Axillary
Abnormalities on actual values					
Normal	≤ 37.8	≤ 38.0	≤ 38.0	≤ 37.2	≤ 38.0
Abnormally high	> 37.8	>38.0	>38.0	>37.2	>38.0

Emergence definition for grades/abnormalities

A grade/abnormality will be considered emergent if it is worse than baseline. If baseline is missing, the grade/abnormality is always considered as emergent. A shift from ‘abnormally low’ at baseline to ‘abnormally high’ post baseline (or vice versa) is also emergent. The emergence definition applies regardless of analysis phase and within each analysis phase.

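### In the vital-sign shift and emergent tables, Section 6.3.2's maximum rule drops low heart and respiratory rates that Section 6.3.1 requires shown, and it ignores the site-specific temperature limits of Table 27

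*SAP*

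**What the plan says.** SAP Section 6.3.1 says that a subject with both a low and a high post-baseline value counts in both directions: "both abnormalities are shown in the tables. This means that the sum of the percentages can be more than 100" per cent. Table 26 supplies low limits for all four age classes: "Heart rate HR (bpm) abnormally low <80 <70 <60 <90" and "Respiratory rate abnormally low <25 <20 <18 <20". The same section counts a shift from low to high, or from high to low, as emergent, and adds: "The emergence definition applies regardless of analysis phase and within each analysis phase".

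Section 6.3.2 describes the summary tables: "A cross-tabulation of the worst grade/abnormality versus baseline will be presented", with counts per worst and per emergent worst category. It then fixes what worst means: "For Respiratory rate, heart rate and body temperature, the maximum value will be considered as the worst grade/value". For oxygen saturation it is the lowest value. Nothing is said for systolic or diastolic pressure. The maximum temperature is taken over on-site and caregiver readings together; measurement site is not mentioned.

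Table 27 sets temperature limits by site. In the order tympanic, forehead, oral, rectal, axillary, the abnormally high row reads "> 37.8 >38.0 >38.0 >37.2 >38.0" (°C).

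**The concern.** The two sections give different codes for the same child. The maximum rule refers to grade as well as value and follows directly on the description of the cross-tabulation, so a programmer would reasonably apply it to the coded category. The tables that compare arms against baseline would then show raised heart and breathing rates but almost never lowered ones. That matters in a trial of infants that lists apneic attacks and arrhythmia among RSV-related complications (Table 22) and has a cardiac list of special interest (Table 24).

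The rest of the SAP handles direction differently. Section 6.2.1 repeats laboratory cross-tabulations separately for low and high limits where the grading list has both. Section 6.4.1 states the both-directions rule for ECG, and Section 6.4.2 adds no maximum rule. Only vital signs carry the override.

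For temperature, a limit that depends on site is applied after a selection that ignores site. The rectal limit, printed well below the other four, invites a separate check.

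**Working it through.** The SAP gives no figure to reproduce. The check is whether the two rules return the same codes.

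**Heart rate and respiratory rate.** Inputs are the Table 26 limits, low L and high H. A value v is low if v < L, high if v > H, otherwise normal. The 6.3.1 rule keeps every abnormal code that occurs. The 6.3.2 rule codes only max(v). Each parameter and age class has two constructed subjects: A with one low and one mid-range value (L − 5 and (L + H)/2), B with one low and one high value (L − 5 and H + 5).

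| Parameter, age | L / H | A: values | A: 6.3.1 → 6.3.2 | B: values | B: 6.3.1 → 6.3.2 |
|---|---|---|---|---|---|
| HR, 0–3 months | 80 / 180 | 75, 130 | low → normal | 75, 185 | low and high → high |
| HR, 3–12 months | 70 / 150 | 65, 110 | low → normal | 65, 155 | low and high → high |
| HR, 1–2 years | 60 / 140 | 55, 100 | low → normal | 55, 145 | low and high → high |
| HR, 2–<3 years | 90 / 130 | 85, 110 | low → normal | 85, 135 | low and high → high |
| RR, 0–3 months | 25 / 70 | 20, 47.5 | low → normal | 20, 75 | low and high → high |
| RR, 3–12 months | 20 / 60 | 15, 40 | low → normal | 15, 65 | low and high → high |
| RR, 1–2 years | 18 / 50 | 13, 34 | low → normal | 13, 55 | low and high → high |
| RR, 2–<3 years | 20 / 35 | 15, 27.5 | low → normal | 15, 40 | low and high → high |

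The low code is kept in 16 of 16 cases (2 parameters × 4 age classes × 2 patterns) under 6.3.1 and in 0 of 16 under 6.3.2. This is general: the maximum is coded low only when max(v) < L, that is, when every post-baseline value in the phase is below L. It follows that a high-to-low shift, which 6.3.1 counts as emergent, can be shown only for a subject whose values are all low.

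**Temperature, order of operations.** Take two readings in one child and phase: tympanic 37.9 and oral 38.0. Tympanic 37.9 > 37.8 is abnormal; oral 38.0 ≤ 38.0 is normal. The maximum is 38.0, oral, coded normal, so the tympanic abnormality is lost. This uses neither the rectal nor the axillary limit. With tympanic and oral readings only, the band at risk is 38.0 − 37.8 = 0.2 °C wide.

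**Temperature, Table 27 as printed.** Axillary limit minus rectal limit: 38.0 − 37.2 = 0.8 °C. A reading above 37.2 and up to 38.0 °C is therefore abnormal if rectal and normal if axillary. The SAP gives no reason for the difference.

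**The case against.** The best defence is that the sections can be read together: 6.3.2 names a single worst value, while 6.3.1 governs which abnormality codes are shown. That reading is possible, but 6.3.2 does not state it, and its wording covers grade as well as value. The text still has to be reconciled.

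A reader might infer that slow heart rates and slow breathing vanish from the report. The SAP does not support that. Section 6.3.2 also provides an incidence table of abnormalities by treatment group, ranges (hence minima) at each scheduled visit, and a listing of abnormal values, unscheduled ones included. Slow heart rate has a second route as well: Table 28 flags ECG RR intervals above 750, 860 and 1000 ms in the three age classes under 2 years, which convert (60,000 ÷ interval) to 80, 69.8 and 60 bpm, close to the Table 26 low limits. The match fails from 2 years (1200 ms is 50 bpm, against a limit of 90). Apneic attacks are collected as adverse events. All of this stands and confines the loss to the shift and emergent-worst tables. Blood pressure is not under the maximum rule, so no loss can be claimed there.

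A reader might also infer that the rectal and axillary columns were swapped and should simply be exchanged. The SAP does not show which limits were intended. The 38.5 °C rectal figure in Attachment 1 is where Grade 2 starts on a drug-fever toxicity scale; it is not an upper limit of normal and says nothing about axillary readings. An example with an axillary reading displacing a rectal one would rest on the limits in question, which is why the check above uses tympanic and oral readings.

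Finally, displacement by site needs mixed sites within one child, and the SAP does not say how often that happens. That limits its size, not the fault in the derivation order.

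**Conclusion.** The point holds within these bounds. For heart rate and respiratory rate, Sections 6.3.1 and 6.3.2 contradict each other. If 6.3.2 is programmed as written, a low value is lost from the worst-versus-baseline and emergent-worst tables unless all post-baseline values in that phase are low. This assumes that the maximum rule governs the coded category in those tables, which is its natural reading.

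For temperature, taking the maximum before applying the site limit can lose an abnormal code, on the assumption that sites are mixed within a child and that the selected reading is coded by its own site. The frequency cannot be derived from the SAP. The 0.8 °C gap between the rectal and axillary limits is an unexplained feature to verify; it is not a demonstrated error.

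Section 6 makes all safety displays descriptive, without formal testing, so no efficacy result or interim decision rule is affected. It is worth correcting because these tables set the arms against baseline, which the incidence table and the listing do not do in the same way.

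**What to change.** - In Section 6.3.2, replace the maximum rule for heart rate and respiratory rate with the worst abnormality in each direction, and show low and high separately as 6.3.1 requires. State that the same applies to systolic and diastolic pressure, for which no direction is now named.
- For body temperature, code each reading against its own site limit first, then take the worst code over the phase.
- Check the rectal and axillary columns of Table 27 against their source. Correct them if they were interchanged, or add a line explaining the lower rectal limit. The check should not presume which limit is right.

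The cost is a few lines of SAP wording, an added row per parameter in existing tables, one change in derivation order and one table check. No new data or assessments are needed.

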6.4. Electrocardiogram

PR, QT, QRS, QTc intervals and heart rate will be investigated. QTcB and QTcF values will be used as reported by the central ECG laboratory, they will not be recalculated. Overall interpretation will be based on the investigator's assessment as captured in the ECG eCRF and categorized as:

- Normal
- Abnormal
- Not evaluable

6.4.1. Definitions

Definitions and Abnormalities

The ECG abnormalities will be defined as indicated in [Table 28](#). ECG abnormalities will be identified based on subject's age at the time of the assessment and as follows:

- Worst grades/abnormalities are determined over the whole observational period and for each analysis phase separately, including post-baseline scheduled and unscheduled measurements of that analysis phase.
- The abnormalities 'abnormally low' and 'abnormally high'/grades are considered equally important, i.e. if a subject has as well an abnormally low as an abnormally high or graded value post-baseline, both abnormalities are shown in the tables. This means that the sum of the percentages can be more than 100%.

Table 28: ECG Abnormalities

Parameter (unit)	Age class	Abnormally low	Abnormally high
PR (msec)	0 - 2 years	NA	>150
	2 - <3 years	<100	>150
QRS (msec)	0 - 2 years	NA	>79
	2 - <3 years	<40	>79
QT (msec)	0 - 2 years	NA	>500
	2 - <18 years	<320	>450
RR (msec)	0 - 3 months	<333	>750
	3 - 12 months	<400	>860
	1 - 2 years	<430	>1000
	2 - <18 years	<600	>1200
Abnormalities on the changes from baseline (ΔQTc)			
		Abnormality Code	Criteria
QT corrected		Borderline QTc change	30 ms < ΔQTc < 60 ms
		Abnormally high QTc change	ΔQTc > 60 ms
Abnormalities on actual QTcF values			
QT corrected Fridericia's Correction Formula	Abnormally high QTcF value		450 ms < QTcF \leq 480 ms
			480 ms < QTcF \leq 500 ms >500 ms

Emergent definition for abnormalities

An abnormality will be considered emergent if it is worse than baseline. If baseline is missing, the abnormality is always considered as emergent. A shift from ‘abnormally low’ at baseline to ‘abnormally high’ post-baseline (or vice versa) is also emergent. The emergence definition applies regardless of analysis phase and within each analysis phase.

TriPLICATE ECG ASSESSMENTS

If not available from the central ECG laboratory: for timepoints on which triplicate ECGs apply (expected for all timepoints), a mean value per triplet cluster, will be calculated per timepoint before any further handling. This mean value will be used through the entire analysis. In the analysis dataset, the time of the first triplet member will be retained for this average record.

Rounding

When ECG parameters have to be derived or any operations have to be performed (e.g. averaging over many assessments/triplicates), no rounding to the integer/unit will be performed; the maximum stored resolution of these derived values in the derived dataset(s) will be limited to 8 decimal positions. When used in tables, these values will be presented using formats reflecting the resolution of the unit applicable to the respective parameter (milliseconds, beats per minute).

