6.4.2. Analysis Methods

Descriptive statistics (mean, standard deviation, median and range) will be provided for the ECG parameters at each scheduled visit. Changes from baseline will be summarized by treatment group. Incidence of ECG parameters that meet criteria for abnormality will be tabulated for each treatment group.

A cross-tabulation of the worst abnormality versus baseline will be presented for the combination of analysis treatment- and follow-up phase and for the analysis treatment phase only. This table will also show the number (n) and percentage (%) of subjects per worst toxicity/abnormality, the number (n) and percentage (%) of subjects per emergent worst toxicity/abnormality.

A tabulation of the worst QT/QTc change versus baseline per treatment for the combination of analysis treatment- and follow-up phase will be presented and for the analysis treatment phase only.

Mean \pm SE graphs over time for the actual values and changes from baseline will be generated and presented by treatment group and by age group as assigned at Screening.

A listing of abnormal individual subject ECG values from scheduled and unscheduled timepoints will be provided. This listing will include all other timepoints for the corresponding subject/parameter. In addition, ECG: Overall interpretation will also be listed.

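### Table 28 codes uncorrected QT against limits that conflict with the SAP's own heart-rate tables, and its QTc change codes name no correction formula

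*SAP*

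**What the plan says.** SAP Section 6.4 carries both QTcB and QTcF as reported by the central ECG laboratory. Section 6.4.1 (Table 28) then defines the abnormality codes:

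- Uncorrected QT under 2 years: "QT (msec) 0 - 2 years NA >500", so there is no low limit.
- Uncorrected QT in the older class: "2 - <18 years <320 >450".
- RR interval in the older class: "2 - <18 years <600 >1200".
- Change from baseline: "Borderline QTc change 30 ms < ΔQTc < 60 ms", with a second code above 60 ms. The row does not name the correction.
- Actual QTc: Fridericia only, in bands above 450, 480 and 500 ms, with no age split.

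Section 6.4.2 tabulates the incidence of these codes by treatment group and adds "A tabulation of the worst QT/QTc change versus baseline per treatment for the combination of analysis treatment- and follow-up phase".

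Section 6.3.1 gives the heart rates for comparison. Table 25 lists the normal ranges for 0-3 months, 3-6 months, 6-12 months, 1-2 years and 2-<3 years: "Heart rate HR (bpm) 100 - 150 90 - 120 80 - 120 70 - 110 95 - 125". Table 26 lists the abnormal limits for 0-3 months, 3-12 months, 1-2 years and 2-<3 years: "Heart rate HR (bpm) abnormally low <80 <70 <60 <90" and "abnormally high >180 >150 >140 >130".

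**The concern.** Uncorrected QT shortens as the heart speeds up, so a fixed limit in milliseconds has meaning only at a given heart rate. The younger class, with the faster hearts, has the looser upper limit (500 ms against 450 ms). At 120 bpm the RR interval is 500 ms, so from that rate upward a QT above 500 ms would be longer than the whole cardiac cycle.

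In the older class the low limit is close to the QT of a child with an unremarkable QTcF at an ordinary toddler heart rate. A drug that lengthened QT would reduce the count of such low flags.

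The change codes leave open a choice between two corrections that move differently as heart rate falls during recovery. QT is a safety focus here: Table 24 lists QT-related cardiac events, and Section 2.1.4 describes ECGs about 1 hour post-dose on Days 1 and 3. Coded rows tabulated by arm should mean what their labels say.

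**Working it through.** The SAP gives no figure on this point to reproduce. The check converts its limits onto one scale.

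**Inputs.** QT and RR limits from Table 28; normal heart rates from Table 25; abnormal heart rates from Table 26.

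**Formulas.** RR (ms) = 60000/HR; QTcF = QT/(RR in s)^(1/3); QTcB = QT/(RR in s)^(1/2).

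**1. RR limits against Table 26.** Under 2 years they agree: 333, 400 and 430 ms are 180, 150 and 140 bpm; 750, 860 and 1000 ms are 80, 70 and 60 bpm. In the 2 to <18 year class they do not. RR <600 ms means above 100 bpm, whereas Table 25 calls 95-125 bpm normal at 2-<3 years and Table 26 sets the limit at >130 bpm. RR >1200 ms means below 50 bpm, against <90 bpm in Table 26. A 2-year-old at 101-125 bpm is normal in Table 25 and abnormally low on RR in Table 28.

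**2. QT limits as QTcF over Table 25 heart rates.**

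| Age | Limit | HR (bpm) | Equivalent QTcF (ms) |
|---|---|---|---|
| 0-3 months | QT >500 | 100-150 | >593 to >679 |
| 3-6 months | QT >500 | 90-120 | >572 to >630 |
| 6-12 months | QT >500 | 80-120 | >550 to >630 |
| 1-2 years | QT >500 | 70-110 | >526 to >612 |
| 2-<3 years | QT >450 | 95-125 | >524 to >575 |
| 2-<3 years | QT <320 | 95-125 | <373 to <409 |

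Example: 500/(60/70)^(1/3) = 500/0.950 = 526.

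In reverse, a child under 2 years with QTcF 500 ms has a QT of 368 ms (150 bpm) to 475 ms (70 bpm), short of the 500 ms limit. More generally, when RR is at most 1000 ms, QTcF is at least as large as QT. So at 60 bpm or faster, every QT above 500 ms is already a QTcF above 500 ms. Only below 60 bpm, which Table 26 codes abnormally low at every age here, could the row add a child.

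**3. The low flag at 2-<3 years.** QT falls below 320 ms when HR exceeds 60 × (QTcF/320)^3. That is about 100 bpm for QTcF 380, 117 bpm for 400 and 136 bpm for 420. The first two lie inside the Table 25 normal range.

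The share of children flagged needs a QTcF distribution, which the SAP does not give. The table assumes QTcF normal with SD 15 ms, and heart rate normal around 110 bpm with SD 7.65 or 11.7.

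| Assumed mean QTcF | Coded low |
|---|---|
| 380 ms | 71-74% |
| 400 ms | 31-34% |
| 420 ms | 5-8% |

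**4. What the unnamed correction can do.** Assume heart rate falls from 150 to 110 bpm. With QTcF constant at 400 ms, QT changes from 295 to 327 ms (+32) and QTcB from 466 to 443 ms (about -23). A true QTcF rise from 400 to 440 ms reads as +21 ms on QTcB, below the 30 ms code. If instead QTcB is held constant at 400 ms, QTcF changes by +18 ms. The choice of formula can therefore decide the code.

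**5. Boundary.** The codes are 30 < Δ < 60 and Δ > 60, so Δ = 60 is in neither.

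**The case against.** The strongest reply is that prolongation is already coded. The QTcF bands in Table 28 apply at all ages and catch every child whom the QT row misses. Section 6.4.2 adds descriptive statistics, graphs by age group and listings, safety is descriptive, and no decision rule in Section 5.6 uses the QT row. This stands. A reader might infer that the plan cannot show QT prolongation under 2 years or gives false reassurance overall; the QTcF rows rule that out.

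A reader might also infer that the change codes hide prolongation during recovery. That would require QTcB alone to be used, which the SAP does not say. Section 6.4 carries both corrections, and the row may be meant for each. The recovery example also assumes which correction is stable; as shown, holding QTcB constant makes QTcF drift. Recovery common to all arms does not bias a randomised comparison, and nothing in the SAP shows that recovery speed differs between arms. What survives is that the code is undefined.

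The same holds for uncorrected QT change. Section 6.4.2 mentions QT/QTc change, but Table 28 has change codes only for ΔQTc, so the label may be generic.

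Finally, the low-flag percentages are assumed, and a single figure such as one third of 2-year-olds is not supported. The number of children aged 2-<3 years is not stated either. An exact 60 ms should be uncommon, because Section 6.4.1 averages triplicates without rounding. These replies limit the consequence. They do not make the QT and RR limits consistent with Tables 25 and 26.

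**Conclusion.** The point holds in a limited form. Under 2 years the QT >500 ms row is redundant: it needs QTcF above 526-679 ms at normal heart rates and cannot flag a child in the 450-500 ms QTcF bands at those rates. At 2-<3 years the QT <320 ms row can label children abnormal who have a normal heart rate and an unremarkable QTcF. Around 110 bpm the share is roughly 5% to 74% for an assumed mean QTcF of 420 down to 380 ms (SD 15). The 2 to <18 year RR limits contradict Tables 25 and 26 outright.

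The change codes lack a named correction and leave 60 ms unclassified. The unit conversions rest only on the SAP's tables and the standard Bazett and Fridericia formulas; the flag rates and recovery examples rest on stated assumptions. The safety analysis as a whole is not blind to prolongation. Some rows tabulated by arm would, if followed as written, be uninformative or misleading.

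**What to change.** - In Table 28, drop the uncorrected QT abnormality row and keep QT in descriptive statistics and listings; or reconcile it with Tables 25 and 26.
- Reconcile the 2 to <18 year RR row with Tables 25 and 26.
- Define the change codes as 30 < ΔQTcF ≤ 60 ms and ΔQTcF > 60 ms. The reason for QTcF is consistency with the actual-value rows of the same table.
- In Section 6.4.2, state that the worst-change tabulation uses QTcF, with QTcB as supplementary if wanted.

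The cost is SAP wording and, if the row is dropped, one abnormality row fewer. No new data are needed, because the central ECG laboratory already supplies QTcF.

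### The ECG RR-interval limits for children aged 2 or over (Table 28) contradict the heart-rate limits for the same age in Tables 25 and 26

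*SAP*

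**What the plan says.** Table 28 (SAP Section 6.4.1) codes the ECG RR interval in ms. The three younger rows read "0 - 3 months <333 >750", "3 - 12 months <400 >860" and "1 - 2 years <430 >1000". The last row reads "2 - <18 years <600 >1200". The uncorrected QT interval uses the same oldest class, "2 - <18 years <320 >450". PR and QRS in the same table use 2-<3 years instead.

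Table 26 (Section 6.3.1) codes vital-sign heart rate in bpm for 0-3 months, 3-12 months, 1-2 years and 2-<3 years. The low limits are "abnormally low <80 <70 <60 <90" and the high limits are "abnormally high >180 >150 >140 >130". Table 25 gives normal ranges in five age classes, the last again being 2-<3 years: "Heart rate HR (bpm) 100 - 150 90 - 120 80 - 120 70 - 110 95 - 125".

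The ECG class follows the child's age at the assessment (Section 6.4.1). An abnormality is emergent if it is worse than baseline, or if baseline is missing. Section 6.4.2 tabulates the codes by treatment group as incidence and as worst abnormality against baseline. Section 6.4 lists heart rate among the ECG parameters, but Table 28 has no heart-rate row, so RR is its only coding of rate.

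**The concern.** RR interval and heart rate are the same quantity on reciprocal scales, so a given rate at a given age should get the same code in the ECG and vital-sign tables. For the three younger classes it does. For the oldest class the ECG limits belong to an age range, 2 to under 18 years, that lies mostly outside a trial enrolling up to 3 years of age.

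At stake is the readability of the ECG rate abnormalities for the oldest children. Rates that the SAP itself calls normal would appear as abnormal in every arm. Slow rates that it calls abnormal would not appear under the ECG RR code. A real worsening could also be masked: a 2-year-old at 110 bpm at baseline is already coded abnormally low RR, so a later 150 bpm, above the Table 26 limit, gets the same code and is not emergent.

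**Working it through.** **Inputs.** RR limits from Table 28; heart-rate limits from Table 26; normal heart-rate range from Table 25.

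**Formula.** Heart rate (bpm) = 60000 / RR (ms). A low RR limit is a high heart-rate limit, and the reverse.

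**Step 1: convert every Table 28 RR row and compare it with Table 26.**

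| Age class (Table 28) | RR limits (ms) | As heart rate (bpm) | Table 26 (bpm) | Difference, fast / slow limit |
|---|---|---|---|---|
| 0-3 months | <333 / >750 | >180.2 / <80.0 | >180 / <80 | 0.1% / 0.0% |
| 3-12 months | <400 / >860 | >150.0 / <69.8 | >150 / <70 | 0.0% / -0.3% |
| 1-2 years | <430 / >1000 | >139.5 / <60.0 | >140 / <60 | -0.3% / 0.0% |
| 2-<18 years | <600 / >1200 | >100.0 / <50.0 | >130 / <90 (2-<3 years) | -23.1% / -44.4% |

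The three younger rows are the Table 26 limits up to rounding. The oldest row is not.

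**Step 2: express the 2-<3 years entries as RR.**
- Table 26: 60000/130 = 461.5 ms and 60000/90 = 666.7 ms, so RR <462 / >667 ms.
- Table 25: 60000/125 = 480 ms and 60000/95 = 631.6 ms, so normal RR is 480-632 ms.

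**Step 3: measure the two zones of disagreement.**
- Fast side: rates above 100 and up to 125 bpm (RR 480 to under 600 ms) are normal in Table 25 and abnormally low RR in Table 28. That is (125 - 100)/(125 - 95) = 25/30 = 83% of the normal range on the bpm scale, or (600 - 480)/(631.6 - 480) = 79% on the RR scale.
- Slow side: rates from 50 to under 90 bpm (RR above 667 and up to 1200 ms) are abnormally low in Table 26 and not flagged in Table 28.

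**Step 4: the QT limit of the same class.** With QT = QTcF x RR^(1/3) (RR in seconds), QT falls below 320 ms once RR is below (320/QTcF)^3. The documents give no typical QTcF, so 380, 400 and 420 ms are assumptions:
- 380 ms: RR 0.597 s, about 100 bpm
- 400 ms: RR 0.512 s, about 117 bpm
- 420 ms: RR 0.442 s, about 136 bpm

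At the first two values some rates within Table 25's normal range would be coded as low QT. At the third none would. This justifies a review of the limit but does not show a contradiction.

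**The case against.** Several points on the other side stand.

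- **Which table is wrong is open.** One might infer that Table 26 is right and Table 28 should follow it. The documents do not support that. The Table 26 low limits run 80, 70, 60 and then 90 bpm, and Table 25 moves from 70-110 to 95-125 bpm at the same step. The Table 28 RR limits rise steadily with age, and nothing in the SAP says they derive from Table 26. The contradiction is certain; the direction of the correction is not.
- **Emergent tables are not flooded.** A reader might expect them to fill with normal rates. A child above 100 bpm both at baseline and later is not emergent, and the worst-versus-baseline table shows the baseline code. The incidence and worst-abnormality tables are distorted more. What remains is the masking of worsening from an already flagged baseline.
- **Slow rates are not lost altogether.** Vital-sign heart rate is still coded with Table 26 in both directions, although Section 6.3.2 takes the maximum heart rate as the worst value. ECG heart rate is summarised and the investigator's ECG interpretation is listed. Only the ECG RR code misses 50-89 bpm.
- **QT safety is not compromised.** The QTcF and change-in-QTc codes have no age class, and the QT-event list is identified by MedDRA term. None of them uses this row.
- **Class change at the second birthday is a weak argument.** Few children can turn 2 in a study of about 29 days each. Limits taken from Table 26 would also create a step, from 1000 to 667 ms on the slow side.

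The step-by-step match in the three younger classes nevertheless makes a deliberate difference between ECG and vital-sign coding unlikely, and the SAP states no reason for one.

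**Conclusion.** The inconsistency is real and exact. The oldest RR row of Table 28 corresponds to above 100 / below 50 bpm, against above 130 / below 90 bpm in Table 26, and it cuts through Table 25's normal range of 95-125 bpm.

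The reach is small. It concerns only children aged 2 or over at the ECG: the 6-subject subcohort plus others whose number is not stated (Section 1.2). The 1-2 years row agrees with Table 26, so younger toddlers are not affected. The analysis is descriptive safety only; efficacy and error rates are untouched.

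The 83% is a share of the normal range, not of children. A reader might take it as the fraction of healthy 2-year-olds who would be flagged, but that would need a heart-rate distribution that the documents do not give. The conclusion rests only on the three tables and the reciprocal conversion; the QT remark rests on the assumed QTcF values.

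**What to change.** Before the ECG outputs are programmed, reconcile the oldest RR row of Table 28 with the 2-<3 years heart-rate entries of Tables 25 and 26, so that one rate at one age gets the same code in the ECG and vital-sign tables. Use a 2-3-year class, as PR and QRS already do. If a difference is intended, state the reason. Check the non-monotone Table 26 low limits (80, 70, 60, 90 bpm) at the same time. The values 462 and 667 ms show only what agreement with Table 26 would mean; they are not a recommended clinical limit.

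Review the uncorrected QT limit of 320 ms from the same class for consistency. It should not simply be dropped in favour of QTcF: Table 28 grades only high QTcF, so no low-QT code would remain for this age.

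The cost is a correction to one SAP table, possibly two, and a programming update. No new data are needed.
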